Following complete PD stone removal, patients will be given a validated quality-of-life instrument, the PANQOL¹⁸, at 1, 3, 6, 12, 18, and 24 months post-treatment. Similarly, the visual analog scale will also be given at 1, 3, 6, 12, 18, and 24 months post-treatment. Lastly, daily opiate use will be recorded at 1, 3, 6, 12, 18, and 24 months post-treatment. The 1, 3, 6, 12, 18, and 24-month assessments will have a ± 2 weeks window to be completed.

In order to ensure that subjects respond to the questionnaires as required, REDCap will be programmed to automatically send three reminders to the participants' email when the questionnaires are due. Furthermore, the study coordinator will make three separate attempts to contact non-responding patients within the designated timeframe. If a patient remains unresponsive, these instances will be documented as protocol deviations.

Documentation on interventions for chronic pancreatitis occurring outside of scheduled appointments will be recorded a separate CRF ("non-scheduled chronic pancreatitis interventions"). This CRF will encompass any pancreatic interventions (other than POP x ESWL planned visits) taking place between the subject's consent form signature and their final follow-up.

All patients will have a HgbA1c and fecal elastase drawn at baseline (within 12 months prior to treatment initiation) and at the 1-year mark from treatment completion. Laboratory tests will be drawn per standard of care, and tests results will be added to the REDCap database.

Figure 1: Study Flowsheet

4. Subject Inclusion and Exclusion Criteria

4.1 *Inclusion Criteria:*

1. Subjects aged 18-89
2. Subjects with abdominal pain secondary to chronic calcific pancreatitis and main pancreatic duct stones found on cross-sectional imaging, EUS, or ERP with upstream PD dilation
3. Main PD stones in the head or body that are greater than 50% in size of the immediate downstream diameter of the pancreatic duct
4. Stones ≥ 5 mm in diameter or impacted in the main PD on cross-sectional imaging or EUS

4.2 *Exclusion Criteria:*

1. Subjects who have previously received PPL or ESWL for PD stones within 12 months of enrollment
2. Patients with PD stones isolated in the tail or side branches of the main duct
3. Pancreatic tail stones comprising more than one-third of the stone burden within the main PD, if multiple locations of stones are noted within the main PD
4. Nontraversable ansa loop with upstream stones

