ESWL will start at the lowest power level and will gradually be increased until 25% of the shocks have been delivered to help create vascular constriction to minimize the risk of hematoma. The middle 50% of the shocks will be equally distributed between the 1st 25% of shocks and the final 25% of shocks at the top level of power. The final 1000 shocks should be administered at the highest power level number. The range of shocks delivered will be limited to 4000 to 6000 shocks. The rate of shocks will range from 70-90/minute.

A KUB (kidney-urether-bladder)-right posterior oblique X-ray will be done within 7 days after the ESWL session to determine the level of fragmentation of the stones. The goal will be to continue ESWL until stone fragments are felt to be \leq 3mm.

Non-lithotripsy panreatoscopy maneuvers will be permitted in the ESWL arm and not result in primary endpoint failure.

5.5 *Outcome Determination*

An occlusion panreatogram following extraction of stone fragments will be obtained after the endoscopist/urologist has determined treatment completion. All patients will receive an ERP at the completion or either PPL or ESWL, with an occlusion panreatogram performed to determine stone

clearance. An initial pancreatogram (or PD image from cross-sectional test – MRCP, MRI, CT scan, or EUS) with stone location and two representative final occlusion pancreatogram images will be uploaded to the REDCap database and will be reviewed by a blinded endoscopist to assess the level of stone clearance (complete or partial).

6. Standard of Care/Research Procedure

The current standard of care for the treatment of PD stones varies by region. In Europe, extracorporeal shock- wave lithotripsy (**ESWL**) is a primary method by which stones are fragmented. Once ESWL is performed, however, ERP is still performed to remove the stone fragments. In Europe, ESWL is frequently performed by gastroenterologists who can perform ERP as well.

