In the United States, however, ESWL is primarily performed by urologists for the treatment of kidney stones. Few gastroenterologists have direct access to ESWL and urologists remain hesitant to use ESWL for non-kidney stones. Therefore, in the United States, standard therapy has become ERP.⁴ In ERP, pancreatography is performed by cannulating the PD and then injecting radio-opaque iodine contrast into the PD. Pancreatography allows for radiographic visualization of a stone and associated strictures; stone removal can be achieved by sweeping the PD with either a balloon or basket after performing a pancreatic sphincterotomy where the sphincter opening the PD is cut and coagulated. This is often followed by balloon or catheter dilation of any downstream pancreatic duct strictures. ERP is typically made more difficult by strictures downstream of the stones and the presence of numerous, large (>5mm in diameter) or hard stones.

In this study, per-oral pancreatoscopy-guided lithotripsy (**PPL**) will be compared with ESWL. Pancreatoscopy, the placement of a small endoscope directly into the PD, allows for direct visualization of the PD and stones. This allows for intraductal lithotripsy to be performed while directly visualizing the stones. Briefly, EHL, one version of intraductal lithotripsy, creates high-frequency shock-wave pulses which generate energy that can result in the fragmentation of stones. LL, on the other hand, involves the focusing of laser light on the surface of a stone which can induce wave-mediated stone fragmentation. Both techniques can fragment stones into smaller pieces, which can then be swept out of the PD using standard techniques such as balloon or basket sweeping.

Upon completion of the procedure, all patients will be observed in the post-anesthesia care unit for 1 hour as is the current standard of care. Following the index ERP session and sphincterotomy, extended recovery in the hospital or discharge will be planned per institutional practice. If patients exhibit symptoms such as intractable abdominal pain or severe N/V, they will be admitted for overnight observation. All patients will receive a phone call within 48 hours of discharge as is standard practice to identify any short-term AE's.

7. Subject and Study Stopping Criteria

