The most common AEs for PPL are expected to include pancreatitis and bleeding. The most common infectious complications are expected to include cholangitis, cholecystitis, and less likely or rare duodenoscope-related infection transmissions and perforation. No differences in the types and proportion of AEs have been found in previous studies examining EHL and LL.¹⁰

The risks of ESWL include post-ESWL pancreatitis, bleeding, infection, steinstrasse, sepsis, and rarely, perforation, pancreatic duct leak and arrhythmias. An overall AE rate for ESWL is 6.7%.²¹ The most common adverse event associated with ESWL remains pancreatitis with a meta-analysis finding a rate of 4.2%.¹⁴ Mild skin erythema and tenderness also typically occurs at the region of contact with the shockwaves and other adverse events such as bleeding and infection occur in approximately 1% of cases.³ Similarly, the primary risk of PPL is pancreatitis which in a meta-analysis was found to occur in 8.7% of cases.¹⁵ Additional risks include incomplete fragmentation of the stone requiring alternative treatment,

stone migration, inability to access stones(s), no stones, need for further procedures, loss of pancreas and/or death. Machine malfunction may occur, necessitating rescheduling. In addition, the stones might not get removed completely. In comparison, surgery, an alternative treatment modality typically consisting of either a lateral pancreaticojejunostomy or a Frey procedure, has a higher rate of adverse events. In a randomized trial comparing surgery with endoscopy, the surgical treatment arm had a 27% adverse event rate with the main adverse events including anastomotic leakage (6.8%), bleeding (6.8%), incisional hernia (4.5%), pneumonia (4.5%), and severe delayed gastric emptying (4.5%).²² Additionally, as these procedures would typically be performed as part of the management of patients with PD stones at the study sites, there are no separate research risks from the risks of standard care.

Worsening abdominal pain may occur after either of the procedures, with the potential need for prolonged observation. Abdominal pain may be related to ductal manipulation, stone mobility, or due to other adverse events.

The definition of a serious AE is any AE that results in any of the following outcomes:

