- 1) death, 2) life-threatening, 3) persistent or significant disability/incapacity, or 4) requires or prolongs hospitalization. Serious AEs are expected to include perforation, air embolism, and cardiopulmonary AEs associated with the use of general anesthesia, which will be used in all procedures.

Unexpected AEs will be defined as any AEs with specificity or severity which is not consistent with the current risk information in this investigational plan as formulated from prior studies investigating the trial interventions.

Grading of severity of AEs will be done in accordance to the grading system proposed by the ASGE and the revised Atlanta classification.^{20, 23} For pancreatitis, grading will be done according to the revised Atlanta classification as follows:

- 1) Mild – no organ dysfunction, 2) Moderate - transient organ failure <48 hours OR local or systemic AEs without persistent organ failure, and 3) Severe – persistent single or multi organ failure >48 hours OR present or persistent systemic inflammatory response syndrome (SIRS).

All other AEs will be classified as follows:

- 1) Mild – AE is usually transient, does not require any special treatment, and does not interfere with the patient's daily activities, 2) Moderate – AE usually introduces a low level of inconvenience or concern to the patient and may interfere with daily activities, but are usually ameliorated with simple therapeutic maneuvers, and 3) Severe – AE interrupts a patient's usual daily activity and generally requires systemic drug therapy or other intervention.

10.2 *Procedures for documentation of adverse events*

All AEs are to be reported using the centralized online data collection system. All AEs must be entered within 14 days of occurrence. A standardized reporting system will be available on the REDCap system, which will be accessible to all study members at each site. AE reporting can be done by either site PIs or research coordinators.

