All serious AEs that occur from initiation of the study to 14 days post final intervention are to be reported immediately (within 24 hours) using the electronic data collection system. All serious AEs will then be immediately relayed to the PIs. The PIs will first review the AEs to: 1) ascertain the seriousness, 2) ascertain the relationship between AE and intervention, 3) verify that all data are complete, and 4) follow-up with the specific site for incomplete data and/or data clarification. The PIs will then submit the AEs to the DSMB, who will then review the AEs to confirm the findings of the PIs.

All AEs from ESWL are ESWL-related. PPL is part of the ERCP procedure. Most AEs in this group will be related to the ERCP procedure itself. A potential rare AE specific to PPL (EHL or LL) is ductal perforation from the lithotripsy fiber and will be noted by the investigator. The investigator will determine the relationship of an AE specific to a lithotripsy device used to fragment the stones.

10.3 *Monitoring of Data*

The DSMB will be responsible for data and safety monitoring. All primary and secondary outcomes as well as data integrity and study progress along with all AEs will be reviewed by the DSMB.

The DSMB will meet at least twice a year to review the data mentioned above. These meetings will every six months.

An interim analysis will be performed at the halfway point of enrollment, which is expected to be at the 75th patient. Should the interim analysis reveal an unexpected accumulation of AEs or a clear superiority of one lithotripsy method over the other, the DSMB may recommend stopping the study, which will be reported to the PIs, IRB and the funding agency.

The DSMB will include at a minimum the following individuals:

- [name]: Gastroenterologist, University of Colorado
- [name]: Hepatologist, University of Colorado
- Biostatistician: Non-study Statistician
- [name]: Gastroenterologist, Beth Israel Deaconess Medical Center

11. Feasibility/Recruitment Plan/Materials

The power analysis suggests that a total of 150 participants will need to be enrolled to achieve sufficient statistical power to compare the two lithotripsy methods. With a total of 8 recruitment sites, we anticipate complete enrollment within 5 years and with a follow-up of 12 months/patient post completion of treatment, the study is anticipated to be completed within 6 years.

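### After the 48-hour call no scheduled contact asks about adverse events, and the serious-AE rule changes at day 14, so the between-arm AE comparison has no common observation window

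*Combined protocol and SAP*

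**What the plan says.** **Serious AEs.** Section 10.2: "All serious AEs that occur from initiation of the study to 14 days post final intervention are to be reported immediately (within 24 hours". Sites enter these reports electronically. The next step is "All serious AEs will then be immediately relayed to the PIs", and after their review "The PIs will then submit the AEs to the DSMB, who will then review the AEs to confirm the findings of the PIs". Neither of these two steps carries a day-14 cut-off of its own, and submission to the DSMB has no stated time limit. The final intervention is not defined, although Section 3 allows up to 4 sessions and then cross-over or combination therapy.

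**All AEs.** Section 10.2: "All AEs must be entered within 14 days of occurrence". No closing date is given. Section 10.3 has the DSMB review all AEs at six-monthly meetings.

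**Contacts.** Section 6: "All patients will receive a phone call within 48 hours of discharge as is standard practice to identify any short-term AE's". Section 3 then schedules assessments at 1, 3, 6, 12, 18 and 24 months; the sentence setting their timing ends "24-month assessments will have a ± 2 weeks window to be completed". Their listed content is the PANQOL, the visual analogue scale and daily opiate use. Section 3 introduces them as following complete stone removal, and the Synopsis counts them from ductal clearance.

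**Use of the data.** The Synopsis lists therapy-related AEs as a secondary endpoint. Section 9 compares overall and serious AE rates between arms by chi-squared or Fisher's exact test and gives no observation window. Sections 7 and 10.3 let the DSMB recommend stopping for an accumulation of AEs.

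**The concern.** A between-arm comparison of harms is interpretable when every randomised patient is asked the same questions over the same period. Here the one AE-directed contact is over within two days of discharge. The next contact is written to collect other outcomes, and only clearly for patients whose duct has been cleared. Some expected complications could arise after the call: for PPL, Section 10.1 names the infectious ones as "cholangitis, cholecystitis, and less likely or rare duodenoscope-related infection transmissions and perforation". Hospital admission makes an event serious under Section 10.1.

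The other records do not clearly fill the gap. The CRF for non-scheduled events in Section 3 covers pancreatic interventions. The hospitalisation outcome in Section 9 is limited to admissions related to chronic pancreatitis, a term it does not define. An admission on day 20 for cholecystitis may fit neither.

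At stake are the completeness of a listed secondary endpoint and the speed with which a late serious event is entered and reviewed.

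**Working it through.** The plan states no figure for this gap, so the check sets its dated rules side by side.

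**Inputs.** Serious-AE cut-off: day 14 after the final intervention (10.2). AE entry: 14 days from occurrence (10.2). Call: within 48 hours of discharge (6). First assessment: 1 month ± 14 days (3). Planned arm size 75; planning clearance rates 70% for ESWL and 90% for PPL (9). AE rates: 6.7% overall for ESWL, 8.7% pancreatitis for PPL (10.1).

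**1. When the first assessment falls.** With a month of m days and clearance on the day of the final intervention, the window is m − 14 to m + 14. Its distance from the day-14 cut-off is (m − 14) − 14 to (m + 14) − 14.

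| m | Window | Distance from day 14 |
|---|---|---|
| 28 | day 14 to 42 | 0 to 28 days |
| 30 | day 16 to 44 | 2 to 30 days |
| 31 | day 17 to 45 | 3 to 31 days |

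If clearance and the final intervention fall on different days, these figures shift.

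**2. Time with no scheduled AE enquiry.** Assume same-day discharge, the call on day 2 and m = 30. The shortest interval is 16 − 2 = 14 days and the longest 44 − 2 = 42 days. This would hold only if the 1-month assessment asked about AEs. As listed, it does not, so the interval has no stated end.

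**3. Whether the 14-day deadline can be met.** An event on day t is due by day t + 14. If the site learns of it on day c, it is already overdue when t < c − 14.
- c = 16: events before day 2 are overdue.
- c = 30: events before day 16 are overdue. A day-3 event was due on day 17 (13 days late) and a day-10 event on day 24 (6 days late).
- c = 44: events before day 30 are overdue.

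Section 10.2 also does not say when the 24 hours for serious AEs start.

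**4. Who has a clearly stated 1-month contact.** At the planning rates, uncleared patients before any cross-over number 75 × (1 − 0.70) = 22.5 for ESWL and 75 × (1 − 0.90) = 7.5 for PPL, or 30 of 150. Section 9 plans an analysis of the same outcomes in partially cleared patients, which implies some follow-up for them, but Section 3 does not schedule it.

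**5. What changes for a serious AE after day 14.** The stated entry deadline goes from 24 hours to 14 days. The duty to enter the event remains, as does DSMB review of all AEs. With six-monthly meetings, that review may wait up to about six months.

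**6. Scale.** Expected counts are small: 75 × 0.067 = 5.0 AEs for ESWL and 75 × 0.087 = 6.5 pancreatitis cases for PPL. These rates measure different things and are not a comparison. They show that one missed event is about 1/5.0 = 20% or 1/6.5 = 15% of such a count. The documents give no time-to-onset data, so the number missed cannot be derived.

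**The case against.** The strongest reply is that nothing is lost. A reader might infer that serious AEs after day 14 have no route to the PIs or the DSMB. The text does not support that: the entry rule is open-ended, the relay sentence has no cut-off of its own, and the DSMB reviews all AEs. Nor does a 24-hour route to the DSMB lapse at day 14, because none is stated even inside the window; the 24 hours govern reporting in the electronic system. A late entry is a missed deadline, and the Section 9 comparison uses all AEs, not only expedited ones. All of this stands.

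A reader might also infer that harms are found more readily after ESWL, which would favour PPL, because an X-ray "will be done within 7 days after the ESWL session to determine the level of fragmentation" and a separate completion ERP bring ESWL patients back. The documents do not show this. The X-ray is done to assess fragmentation, with no AE enquiry attached, and could be taken on day 1. Section 5.5 calls for an ERP at completion in both arms, and no interval between ESWL and that ERP is given. Where the ERP is the final intervention, the contacts that follow are the same as after PPL. PPL patients too may have up to 4 sessions, each with its own call. Any shortfall in follow-up of uncleared patients could act the other way, since the planning rates put more of them in the ESWL arm.

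Finally, no figure in the documents shows that 14 days is too short for expedited reporting. That is fair. What remains is that a rule requiring entry does not create a contact at which the event is discovered.

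**Conclusion.** The point holds as one about eliciting harms and defining the window. After the 48-hour call, capture of AEs rests on spontaneous report. The first later assessment comes at about day 16 to 44, is not written to ask about AEs, and is not clearly scheduled for uncleared patients. From day 14 after an undefined final intervention, the stated serious-AE deadline loosens from 24 hours to 14 days from occurrence, and a site that learns of an event later than that cannot comply. The AE and serious-AE comparison therefore has no common observation window.

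The day count assumes a 30-day month and that clearance and the final intervention coincide. The share of events missed, and the size and direction of any difference between arms, are unknown. The change is worth making because it is cheap and AEs are a listed secondary endpoint; no demonstrated bias is claimed.

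**What to change.** - **Section 3:** add a short fixed set of AE and hospital-contact questions to the 1-month contact, identical in both arms, for every randomised patient whether cleared or not.
- **Section 10.2:** define the final intervention, including after cross-over or combination therapy. Run the AE and serious-AE entry deadlines from site awareness. State the serious-AE reporting rule that applies after day 14, for example the same expedited rule through the 1-month contact. That end point is one workable option; the documents do not establish a particular day.
- **Section 9:** base the between-arm AE and serious-AE comparison on one common window, through the 1-month contact after the defined final intervention.

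The cost is amendment wording, one short form, and a 1-month contact for uncleared patients where none is now clearly scheduled. Sites will process somewhat more AE and serious-AE reports, some due to the underlying disease.

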Primary Endpoint	Main pancreatic duct stone complete clearance rate
Secondary Endpoints	
 • Change in quality of life • Change in pain scores • Change in opiate use • Number of procedures • Adverse Events related to therapies
Study Design	Multicenter randomized trial
Sample Size	150 patients

List of Abbreviations

PD: pancreatic duct

PPL: per oral panreatoscopy-guided lithotripsy

ESWL: extracorporeal shock-wave lithotripsy

EHL: electrohydraulic lithotripsy

LL: laser lithotripsy

ERP: endoscopic retrograde pancreatography

ERCP: endoscopic retrograde cholangiopancreatography

AE: adverse event

EUS: endoscopic ultrasound

CT: computed tomography

MRCP: magnetic resonance cholangiopancreatography

KUB: kidneys-ureters-bladder radiograph

Study Protocol

1. Research Questions and Hypothesis

Pain relief poses a significant challenge in patients with chronic pancreatitis given the paucity of effective medications and interventions. Approximately 50-90% of patients with chronic pancreatitis develop pancreatic duct (**PD**) stones which can obstruct the PD, causing ductal hypertension that can lead to severe pain.¹ This pain is frequently treated with opiates, which not only pose a risk of addiction but are also associated with increased hospitalization rates.² Traditional methods to remove PD stones include endoscopic retrograde pancreatography (**ERP**) with sphincterotomy, stricture dilation, and balloon or basket extraction and extracorporeal shock-wave lithotripsy (**ESWL**) for larger stones.^{3, 4} A potential benefit of ERP techniques over ESWL alone is the ability to treat underlying pancreatic duct strictures with therapeutic PD stenting to not only facilitate stone removal but potentially to help reduce stone recurrence by improving pancreatic juice flow.^{5, 6} As shown previously, use of ESWL alone without treatment of strictures is associated with a significantly higher stone recurrence rate.⁷ Furthermore, ESWL does not remove stone fragments and ERP techniques are required for this aspect of stone clearance.⁸ If ERP with PPL is performed it may obviate the need for ESWL except in special circumstance such as significantly impacted pancreatic stone burden in the head of the pancreas.

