Statistical Analysis: Comparison of technical success rate, defined as the rate of complete clearance of PD stones, between PPL and ESWL will be performing using the chi-squared test or Fisher's exact test. Secondary outcomes including adverse event (both overall and serious adverse event) rates, procedure length, and number of procedures will be compared using a chi-square test or Fisher's exact test for categorical variables and the Student's t test will for continuous variables. A p value <0.05 will be considered significant. In the primary analysis, all results will be analyzed under an intention-to-treat protocol. A per-protocol (secondary) analysis will also be performed where the technical success will be attributed to the combination of modalities resulting in achieving the primary outcome should cross-over occur.

To identify predictors for technical success, a multivariable logistic regression will be performed incorporating variables that were associated ($p<0.2$) with technical success on univariate analysis.

In terms of secondary outcomes, change in PANQOLI scores, VAS scores, and opiate daily doses will be compared between subjects in the PPL group and ESWL group. Additional outcomes to be measured include stone recurrences and number of chronic pancreatitis-related hospitalizations during the follow-up period. Should cross- over occur, under the primary (intention-to-treat) analysis, the outcomes will be attributed to the initially randomized intervention. In the secondary (per-protocol) analysis, the outcomes will be attributed to the combination of treatments resulting in technical success. A subgroup analysis will also be performed on patients who achieved only partial stone clearance (thus considered a treatment

failure) in the above-mentioned outcomes. Comparisons will be made using a chi-squared test or Fisher's exact test for categorical variables and the Student's t test for continuous variables. Paired t tests will be performed to evaluate individual changes within each arm. A p value <0.05 will be considered significant.

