Power analysis: A large meta-analysis by Moole et al found a complete stone clearance rate of 70% in patients who received ESWL in conjunction with ERCP.¹⁴ In contrast, the largest studies examining pancreatoscopy-guided lithotripsy methods have found complete stone clearance rates ranging from 83-99%.^{6,17} Using a conservative stone clearance rate of 90% for pancreatoscopy- guided lithotripsy, a sample size calculation was performed using a two-sided test with 80% power and significance (α) of 0.05. This demonstrated the need for 124 subjects total, with 62 in each arm. Accounting for an expected dropout rate of 20%, the sample size needed would be a total of 150, or 75 subjects in each arm.

10. Data and safety monitoring plan

A Data and Safety Monitoring Board (DSMB) will be established to monitor the data and safety of this project. A DSMB will be appointed by the study team and will include at a minimum: A senior faculty member clinician with substantial research experience within the Division of Gastroenterology and Hepatology at the University of Colorado who is not involved in the study, and will serve as the group leader, a statistician, and a senior gastroenterologist from a non- participating academic institution. The DSMB will meet every six months. DSMB meetings will be only open to designated DSMB staff and other individuals who have been approved to have access to unblinded data. Any recommendations for alteration or termination for part or all of the trial shall be based on consideration of the accumulating data in the context of totality of evidence. Specific statistical monitoring guidelines for safety and efficacy concerning the primary and secondary endpoints will be developed in cooperation with the DSMB.

10.1 *Definition of AEs, serious AEs, and unanticipated problems*

AEs are defined as any undesired, harmful, or pathological change in a patient as indicated by signs, symptoms, or laboratory changes that occur in association with the use of the trial interventions, whether considered intervention-related or not. This definition includes intercurrent illness or injuries, exacerbation of existing conditions, psychological events, psychosocial events, and AEs as a result of the study intervention. All endoscopic AEs will be defined and classified as recommended by the American Society for Gastrointestinal Endoscopy (ASGE).²⁰

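### Section 10.2 attributes adverse events differently in the two arms, which would favour PPL if the Synopsis endpoint of therapy-related events is counted by that rule

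*Combined protocol and SAP*

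**What the plan says.** Four parts of the protocol bear on how safety is counted.

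- **Attribution (Section 10.2).** For ESWL and PPL in turn: "All AEs from ESWL are ESWL-related. PPL is part of the ERCP procedure". On the PPL group it continues: "Most AEs in this group will be related to the ERCP procedure itself". One lithotripsy-specific event is named: "A potential rare AE specific to PPL (EHL or LL) is ductal perforation from the lithotripsy fiber and will be noted by the investigator". The judgement is left to the site: "The investigator will determine the relationship of an AE specific to a lithotripsy device used to fragment the stones".
- **Endpoint (Synopsis).** The secondary endpoints include "Adverse Events related to therapies".
- **Analysis (Section 9).** "Secondary outcomes including adverse event (both overall and serious adverse event) rates, procedure length, and number of procedures will be compared", under intention-to-treat, by chi-squared or Fisher's exact test. Relatedness is not mentioned.
- **Definition (Section 10.1).** Adverse events are counted "whether considered intervention-related or not".

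On exposure, Section 5.5 says: "All patients will receive an ERP at the completion or either PPL or ESWL". ERP is therefore part of the treatment course in both arms.

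**The concern.** Two features of the plan combine.

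First, the attribution text is not symmetric. Events from ESWL are charged wholly to ESWL. For PPL, the protocol states before any event has occurred that most will belong to ERCP. A difference in exposure does not justify this, because ESWL patients also have an ERP. Section 10.2 does not say where an event from that ERP goes.

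Second, attribution may reach an endpoint. The Synopsis words the safety endpoint as related events, Section 9 analyses all events, and nothing says which governs. Whoever reports the Synopsis endpoint would look to Section 10.2 for the meaning of related, since it is the only place that says how events are tied to each therapy.

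At stake is the safety half of the comparison. The trial's hypothesis is that PPL is superior, and a related-event count under Section 10.2 would lean the same way. The judgement rests with the investigator. Section 5.5 provides blinded review for pancreatograms, but no blinded review is stated for adverse events.

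**Working it through.** The documents give no figure for this point, so there is nothing to reproduce. The check first compares the texts, then asks how large the effect would be under the unfavourable reading.

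**Step 1: does attribution enter the comparison?**

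| Place | What is counted | Does attribution matter? |
|---|---|---|
| Synopsis | events related to the therapies | yes |
| Section 9 | all AEs and serious AEs, by randomised arm | no |
| Section 10.1 | all AEs, related or not | no |
| Section 10.2 | relatedness, worded differently by arm | supplies the rule |

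Under Section 9 the shift is zero. Steps 2 and 3 apply only if the Synopsis endpoint is counted as lithotripsy-related events and ERCP-attributed events in the PPL group are left out.

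**Step 2: direction.** Let f be the share of PPL events assigned to ERCP and not counted. The counted PPL rate is p(PPL) × (1 − f), and the ESWL rate is unchanged. The documents do not give f, so a range is shown.

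Section 10.1 gives pancreatitis rates of 8.7% for PPL and 4.2% for ESWL. Section 9 plans 75 patients per arm.

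- f = 0: 75 × 0.087 = 6.5 cases against 75 × 0.042 = 3.2.
- f = 0.50: 8.7% × 0.50 = 4.35%, or 3.3 cases against 3.2.
- f = 0.75: 8.7% × 0.25 = 2.2%, or 1.6 cases against 3.2.
- Break-even: f = 1 − 4.2/8.7 = 0.517.

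The direction therefore reverses once f passes about 52%. Section 10.2 expects most PPL-group events to be ERCP-related, which means more than half, so its own wording puts f close to or beyond this point.

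**Step 3: false-positive risk.** Assume the same true event rate p in both arms, 75 per arm, and two-sided 0.05. The two binomial distributions, with rates p(1 − f) and p, were enumerated exactly. The probabilities of significant results favouring PPL were then added up. The chi-squared test is uncorrected.

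| Share of PPL events counted (1 − f) | p = 8.7%: chi-squared | p = 8.7%: Fisher | p = 6.7%: chi-squared | p = 6.7%: Fisher |
|---|---|---|---|---|
| 50% | 19% | 10% | 15% | 7% |
| 25% | 43% | 27% | 33% | 16% |
| 10% | 67% | 46% | 53% | 28% |

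With every PPL event counted (f = 0) and p = 8.7%, the chi-squared chance of a significant result favouring PPL is 2.6%, as it should be.

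Both values of p are borrowed from Section 10.1: 8.7% is the PPL pancreatitis rate and 6.7% the overall ESWL rate. Each is applied to both arms as an assumption. The two are not like for like, and no overall PPL rate is given.

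**The case against.** The strongest reply is that the analysis section already does the right thing. Section 9 compares overall and serious event rates by randomised arm, and Section 10.1 counts events regardless of relatedness. Section 10.3 has the DSMB review all AEs. This stands: the Section 9 comparison is unaffected by Section 10.2.

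A reader might infer that the attribution rule biases the safety endpoint as the plan stands. The documents do not support that, for three reasons.

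- The text speaks of events from ESWL, not of every event in the ESWL arm. If ERP events in that arm were also set aside, the tilt would be smaller than shown.
- Nothing says that ERCP-attributed events are dropped from a PPL count. Section 10.2 itself makes PPL part of ERCP, and Section 10.1 calls pancreatitis the primary risk of PPL. An ERCP-related event could thus still count as related to the PPL therapy. For the same reason, a scenario with no PPL-related pancreatitis at all is an extreme, not the expected case.
- The sentence on the PPL group can be read as an expectation and not as an instruction.

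A reader might also infer that DSMB oversight is distorted. The relatedness review in Section 10.2 concerns serious events, and the DSMB also sees all events. No distortion is shown.

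What the reply does not remove is that the Synopsis and Section 9 describe different safety endpoints, with no statement of which governs. Under a natural reading of the Synopsis, the Section 10.2 wording would tilt the result.

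**Conclusion.** The concern holds conditionally. The plan contains an attribution rule that differs by arm and says nothing about ERP events in the ESWL arm, and its safety endpoint is described inconsistently. The comparison specified in Section 9 is sound on this point.

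The bias towards PPL arises only if the Synopsis endpoint is counted as lithotripsy-related events under Section 10.2, with ERCP-attributed PPL events excluded and all ESWL events retained. In that case the direction of the pancreatitis difference reverses once about 52% of PPL cases are assigned to ERCP. With equal true rates of 8.7%, the chance of a false significant finding for PPL runs from 19% to 67% by chi-squared, or from 10% to 46% by Fisher, as the counted share falls from 50% to 10%. The counted share and the common event rate are assumptions.

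This concerns a secondary safety endpoint and does not touch the primary one. It should still be settled before data are seen, because the choice of reading could change the safety conclusion.

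**What to change.** - **Synopsis.** Align the safety endpoint with Section 9: any AE and any SAE by randomised arm, covering every procedure of the assigned strategy, including ERP in both arms.
- **Section 10.2.** Replace the arm-specific sentences with one relatedness rule for both arms, namely relationship to any procedure of the assigned strategy. This also settles where ERP events in the ESWL arm go.
- **Device attribution.** Keep events specific to a lithotripsy device, such as fibre perforation, as a descriptive item outside the between-arm comparison.

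The cost is wording in the Synopsis and Section 10.2, with no new data. The downside for the sponsor is that PPL's reported profile of related events may look less favourable than under the present text.
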